D.1.2. Initial screening: All participants will undergo a cLBP screening interview using the recently developed research standards for defining cLBP proposed by the Research Task Force of the NIH Pain Consortium.⁹⁰ This will involve a review of each participant's UAB electronic medical record to confirm cLBP status and assess the reported duration of cLBP, current and past treatments for cLBP, comorbid conditions, and current medication use. Using the joint clinical practice guidelines from the American College of Physicians and the American Pain Society,⁵⁸ patients with cLBP will be placed into 1 of 3 broad categories: 1) nonspecific cLBP, 2) cLBP potentially associated with radiculopathy or spinal stenosis, or 3) cLBP potentially associated with another specific spinal cause. Patients placed into category 3 will be excluded if the cause of cLBP is determined to be ankylosing spondylitis, cancer or other malignancy, or in the context of autoimmune disease or other widespread pain condition (e.g., lupus, fibromyalgia). The screening will also assess demographic, SES, and health history information to ensure that no other exclusion criteria are

[figure not shown]

Figure 7: Flow diagram depicting matriculation through the study protocol.

present. To ensure that a relatively equal number of Blacks and Whites with high and low SES are recruited, a stratified sampling approach will be incorporated for recruitment. This will be done by determining whether a participant falls above or below the poverty line (as a proxy for overall SES) based upon reported annual household income and number of occupants residing within the family/household using the 2015 HHS poverty guidelines.¹⁰¹ In 2015 Alabama was the 6th poorest state in the Union, with 13% of Whites and 31% of Blacks living below the poverty line.¹⁰² Therefore, we are confident in our ability to recruit individuals with high and low SES.

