D.2.2. Biomarker measures: All blood will be collected by research nurses at the UAB Clinical Research Unit prior to quantitative sensory testing. Vitamin D and CRP assays will be performed by the Physiology and Metabolism Core of the UAB University-Wide Interdisciplinary Research Centers (UWIRC) Program under the direction of [name]. Blood samples will be mailed to [name] at Indiana University for assay of oxytocin. **Vitamin D assay:** Following blood collection and processing, serum will be stored in a -80 degree freezer. Serum 25(OH)D analysis will be completed by high performance liquid chromatography (total 25-hydroxyvitamin D = 25(OH)D2 plus 25(OH)D3) and enzyme immunoassay (Cayman Chemical) within six months of the date of collection. Clinical laboratory assessment of serum 25(OH)D best characterizes vitamin D status because it reflects vitamin D synthesized cutaneously as well as through dietary intake. Results of 25(OH)D testing will be shared with participants and if levels are found to be ≤ 30 ng/mL, they will be encouraged to discuss the result with a primary care provider. **Plasma oxytocin assay:** Plasma samples for the detection of oxytocin will also be collected, processed, and stored in a -80 degree freezer. Plasma oxytocin analysis will also be completed using high performance liquid chromatography with sample extraction and enzyme immunoassay (Cayman Chemical) within six months of the date of collection. It has been suggested that sample extraction and enzyme immunoassay may be the most appropriate way to accurately assess plasma oxytocin.¹¹⁵ These assays are specific to oxytocin, but not vasopressin. **High sensitivity C-reactive protein (CRP):** Plasma samples for the detection of CRP will also be collected, processed, and stored in a -80 degree freezer. High sensitivity CRP was be quantified using Cayman Chemical CRP (human) ELISA Kits, which is an immunometric assay that can be used to measure CRP in plasma without prior sample purification.

The assay has a range from 46.9-3,000pg/ml and a limit of detection of approximately 46.9pg/ml.

D.2.3. Psychosocial questionnaires: The **Center for Epidemiological Studies – Depression Scale (CES-D)** measures symptoms of depression and is reliable and valid in both general and clinical populations.¹¹⁶

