D.6.2. Data analysis: Data analysis will begin with calculating and comparing measures of central tendency (sample mean, sample median) and dispersion (sample variance, interquartile range) for all cLBP outcomes (e.g., PROMIS pain intensity, GCPS, ODI) as well as other study variables (CPM and TS, oxytocin, vitamin D, CRP levels, sleep, Perceived Injustice, Experiences of Discrimination, CES-D, etc.) according to race by SES groups. Confounding variables may include age, sex, pain medication use, engagement in treatments during the 4 week follow up period, and others as appropriate and will be considered as statistical controls.

Specific Aim 1: General Linear Models incorporating a 2x2 factorial design for Analysis of Covariance (ANCOVA) will be used to examine race by SES differences in cLBP outcomes including pain severity, disability, and functional performance. Race will include Blacks and Whites, while the Hollingshead Index will comprise the primary SES measure with participants split into high versus low SES according to previously published work.^{134,135} Significant interaction effects will be probed using pair-wise contrasts with Bonferroni-adjusted alpha levels to examine differences across racial and SES groups, with emphasis on low SES Blacks compared to high SES Whites. Additional

Table 5: Sample sizes needed to detect hypothesized race by SES differences in cLBP severity, perceived disability, and functional performance with $p < .05$ and power = .85.

Effect size (f)	Sample size needed
Clinical pain severity	.24
Perceived disability	.19
Functional performance	.21

analyses will be completed considering other indicators of high and low SES including subjective social status (MacArthur) and neighborhood SES. This will be done to determine which aspects of SES are most relevant to consider when addressing cLBP outcomes.

Specific Aim 2: The hypotheses that comprise this aim suggest that pain-relevant biopsychosocial factors including endogenous pain modulation, biomarkers, sleep, and psychosocial functioning will also differ according to racial and SES groups. These hypotheses will be tested using 2x2 ANCOVAs in the same manner indicated in Specific Aim 1. Significant race by SES interactions will be probed using pair-wise contrasts adjusted for multiple comparisons.

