Specific Aim 3: The analytic strategy is designed to test the hypothesis that the biopsychosocial factors included in this study will differentially predict cLBP outcomes in Blacks compared to Whites, and furthermore that the strength of prediction will vary according to high versus low SES. We will use a multiple regression framework to build separate models for Blacks and Whites. Within these models, SES will be included as an effect moderator when examining the associations of biopsychosocial predictors (independent variables) with cLBP outcomes (dependent variables). To illustrate how models will be built and data used, we offer examples. Separate models will be built for Blacks and Whites to determine whether endogenous pain modulatory processes (e.g., CPM and TS) predict functional performance (e.g., SPPB and TUG). Within each model the SES variables will be added to examine interaction effects (i.e., moderation), such that the strength of prediction between endogenous pain modulation and functional performance will be greatest for those with low SES. The same process will be used to examine whether aggregated actigraphic sleep and diary data differentially predicts pain in everyday life (e.g., average ratings of pain intensity collected across 4 weeks of follow up) according to race and SES.

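### Season of blood draw is not a named covariate for serum 25(OH)D: it adds modest noise to the Aim 2 comparison, and biases it only if draw months differ between race by SES cells

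*Combined protocol and SAP*

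**What the plan says.** **Timing of the draw.** D.2.2 sits under experimental session 1 and states: "All blood will be collected by research nurses at the UAB Clinical Research Unit prior to quantitative sensory testing". The descriptions of session 2 (D.4) and of follow-up (D.5) do not mention blood. A single draw per person is therefore an inference, though a natural one. The only date rule for vitamin D is that the assay is done "within six months of the date of collection". That limits storage time and says nothing about time of year.

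**Reason for the marker.** D.2.2 prefers serum 25(OH)D because it "best characterizes vitamin D status because it reflects vitamin D synthesized cutaneously as well as through dietary intake".

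**Use in the analysis.** D.6.2 lists the variables to be summarised, among them "CPM and TS, oxytocin, vitamin D, CRP levels, sleep, Perceived Injustice, Experiences of Discrimination, CES-D, etc.) according to race by SES groups". Biomarkers fall under Specific Aim 2, where "These hypotheses will be tested using 2x2 ANCOVAs in the same manner indicated in Specific Aim 1". Specific Aim 3 tests whether "the biopsychosocial factors included in this study will differentially predict cLBP outcomes in Blacks compared to Whites". Aim 2 counts biomarkers among the biopsychosocial factors, so vitamin D belongs to Aim 3 by implication, although Aim 3 does not name it.

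**Covariates.** D.6.2 says: "Confounding variables may include age, sex, pain medication use, engagement in treatments during the 4 week follow up period, and others as appropriate". These are to be considered as statistical controls. Season and date of draw are not named.

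**Recruitment.** D.1.2 stratifies on race and on the poverty line. Nothing balances enrolment dates across the groups.

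**The concern.** If part of the 25(OH)D level comes from synthesis in the skin, a single value depends partly on the time of year it was taken. Two consequences need to be kept apart.

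- **Noise.** If draw dates are spread over the year, seasonal variation enters the error term of the Aim 2 comparison whether or not the groups are balanced by calendar. A term built from the collection date can remove it.
- **Bias.** If some race by SES cells are sampled more in summer than others, part of the calendar difference appears as a race or SES difference. The comparison is not randomised, so the design does not protect against this, and no check is planned.

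At stake is how precise, and possibly how correct, one Aim 2 conclusion is: whether vitamin D differs by race and SES. The Aim 1 outcomes do not involve vitamin D.

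**Working it through.** **The plan's own figure.** No sample size, SD or effect size is given for vitamin D. The one power figure is N = 240 for the Aim 1 interactions (D.6.1: alpha .05, power .85, smallest f = .19). With a noncentral F for a 1-df interaction in four cells, f = .19 exactly needs 251, and N = 240 gives power 0.834. Values of f that round to .19 (.185 to .195) need 265 down to 239, so 240 fits the rounding. This point does not rest on that figure.

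**Assumptions, because the documents give none.** Season follows an annual sine curve with a peak-to-trough swing of 4, 8 or 12 ng/mL. The between-person SD apart from season is 10 ng/mL. Draw dates are spread over the year. Write A for half the swing.

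**Formulas**
- Share of variance due to season: R² = (A²/2) / (A²/2 + 10²)
- Cut in standard error from adjusting: 1 − √(1 − R²)
- Summer-half mean minus winter-half mean: (4/π)A
- False group difference: difference in summer share × (4/π)A
- d: that difference divided by √(A²/2 + 10²)

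| Swing (ng/mL) | A | R² | Cut in SE | (4/π)A | False difference, 60:40 v 40:60 | d |
|---|---|---|---|---|---|---|
| 4 | 2 | 2/102 = 2.0% | 1.0% | 2.55 | 0.20 × 2.55 = 0.5 | 0.05 |
| 8 | 4 | 8/108 = 7.4% | 3.8% | 5.09 | 0.20 × 5.09 = 1.0 | 0.10 |
| 12 | 6 | 18/118 = 15.3% | 7.9% | 7.64 | 0.20 × 7.64 = 1.5 | 0.14 |

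**Noise expressed as power.** Borrow f = .19 from Aim 1 for illustration, with N = 240 and two season terms. If season explains 2%, 5%, 10% or 20% of within-group variance, power moves from 0.834 to 0.842, 0.853, 0.871 or 0.906.

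**Bias expressed as false-positive rate.** Take swings of 0.4 to 1.0 SD and a 20-point difference in summer share:
- race main effect, 120 v 120, nominal 0.05: 0.068 to 0.166
- interaction with one cell shifted, nominal 0.05: 0.054 to 0.078
- one 60 v 60 contrast, nominal 0.05/6 = 0.0083: 0.011 to 0.026

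Over imbalances of 10 to 30 points the ranges are 0.054 to 0.314, 0.051 to 0.114 and 0.009 to 0.054.

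**If draw dates are unrelated to group.** In 20,000 simulated trials for each of two swings, 0.6 and 1.0 SD, the false-positive rate for the interaction was 0.051 and 0.049. Season is then noise only.

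**How unusual the imbalance would be by chance.** With 60 per cell, the SD of a difference in summer share is √(2 × 0.25/60) = 0.091. A 20-point difference is 0.20/0.091 = 2.2 SD.

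**The case against.** **The covariate list is open.** It is expressly illustrative and would allow a season term. That is correct, but allowing a term is not committing to it. The biological reason for this one is in D.2.2, so it can be named in advance instead of being chosen after the group means are seen.

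**Calendar imbalance is not shown.** A reader might infer it from the poverty rates in D.1.2, "with 13% of Whites and 31% of Blacks living below the poverty line". Those rates bear on how fast groups might fill, not on which months they fill in, and a group that fills slowly over whole years is balanced by season. The documents give no enrolment calendar. Recruitment is stratified on the poverty line while the analysis cells use a Hollingshead split, so filling rates for one do not carry over to the other. This objection stands: bias is a possibility that the plan leaves open, not one it demonstrates.

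**Larger effects can be produced, but only from extreme splits.** At 75:25 against 25:75 the false difference would be 0.50 × (4/π)A = 1.3, 2.5 or 3.8 ng/mL, with d up to about 0.35. A split of that size is 0.50/0.091 = 5.5 chance SDs and would need a systematic cause that the documents do not supply.

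**Aim 3 slopes.** A reader might also infer that omitting season weakens the Aim 3 slopes by R², that is 2% to 15%. That holds only if a person's usual level is the intended exposure. The plan speaks of vitamin D status without saying usual or current, and several outcomes lie close in time to the draw: pain over the past 7 days, function at session 2, and four weekly calls. If current status is the exposure, seasonal variation is signal. This objection also stands.

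**Conclusion.** The omission is real and its certain effect is modest. The documents support four facts: blood is described only at session 1, 25(OH)D is said to reflect synthesis in the skin, vitamin D is compared across race by SES groups, and no season or date term is named. The step from skin synthesis to season, and the size of the seasonal swing, are assumptions.

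Under those assumptions, leaving season out costs between almost nothing and about 8% of the standard error in the Aim 2 vitamin D comparison. Bias is conditional on draw months differing between cells, and even a 20-point difference in summer share gives a d of only about 0.05 to 0.14. The documents do not support saying that the vitamin D contrasts are biased or that the Aim 3 slopes are attenuated. The change is worth making because it is cheap and because a calendar artefact would be awkward to rule out afterwards in a study of disparities.

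**What to change.** In D.6.2:

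1. **Aim 2.** Pre-specify season of draw as a covariate in the ANCOVA for 25(OH)D, either as annual sine and cosine terms of the collection date or as calendar quarter.
2. **Balance.** Tabulate month of draw by race by SES cell, so that a reader can see whether calendar imbalance occurred.
3. **Aim 3.** In models that use vitamin D, include the same terms as a sensitivity analysis, and state whether usual or current vitamin D status is the intended exposure.

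**Cost.** SAP wording only. The collection date must already be held in order to apply the six-month assay limit. The terms use 2 degrees of freedom (sine and cosine) or 3 (quarters). In Aim 2 that is out of about 240 − 4 = 236. In Aim 3 the models are fitted separately by race, so it is out of about 120 people per model. The sample size, visits and procedures do not change.

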D.2.4. Endogenous pain modulation: All participants will undergo quantitative sensory testing for assessment of endogenous pain modulation using painful heat, mechanical, and cold stimuli in a laboratory session lasting approximately 2 hours. **Heat Testing Procedures:** Thermal stimuli will be delivered to the lumber region (i.e., most affected pain site) and to the non-dominant forearm, in randomized order, using a Medoc Pathway Thermal Sensory Analyzer (Ramat Yishai, Israel). Temporal summation of heat pain will involve brief repetitive suprathreshold thermal stimuli. The stimulus parameters for the heat testing procedures will be based on extensive experience in our laboratory and our previously published work.^{92,122,123} **Punctate Mechanical Pain:** Punctate mechanical pain will be assessed at the lumber region (e.g., over erector spinae muscles) and the dorsal aspect of the non-dominant hand using a nylon monofilament (Touchtest Sensory Evaluator 6.65) calibrated to bend at 300g of pressure. As in our previous studies, participants will provide a pain rating following a single contact of the monofilament, after which they will provide another pain rating following a series of 10 contacts at a rate of one contact per second.^{92,122,123} The percent change (increase) between pain ratings for the single versus multiple contacts reflects temporal summation of mechanical pain. **Conditioned Pain Modulation (CPM):** CPM will be used to assess pain inhibitory function. The conditioning stimulus will be the cold pressor task (Thermo Scientific) applied to the dominant hand, which will be tailored for each participant to achieve a stimulus that produces moderate pain (i.e. a rating of 40-60 on the 0-100 scale) and can be tolerated for a 60-second period. The test stimulus will be algometry (Algomed, Medoc, Ramat Yishai, Israel) to assess pressure pain applied to the lumbar region and opposite ventral forearm. The CPM protocol will be conducted according to previously established protocols.^{56,124} First, baseline PPTs will be assessed, after which the participant will immerse their hand in the cold water bath for 60 seconds and immediately afterwards PPTs will again be assessed at the testing sites. In order to operationalize CPM, percent change in PPTs from baseline will be calculated according to the following formula: $[(\text{conditioned PPT} - \text{test PPT}) / \text{test PPT}] * 100$.²⁹ Higher percentages will reflect greater pain inhibition.

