D.5.1. Follow-up component – predicting pain in daily life: As a component of Specific Aim 3 and to translate the laboratory findings to participants’ daily environment, all participants will be contacted by phone once per week for four weeks following completion of study session 2. Participants will be asked to report on symptoms of pain (average and worst intensity), mood, sleep, disability, and interference of pain with daily activities over the preceding week using appropriate PROMIS items banks.¹¹¹ We have successfully used a similar approach in a previous project to collect weekly follow up data.⁹² Given that racial group differences in follow up data could be attributed to differences in treatments received or in comorbidities since completion of the experimental sessions, we will collect this information and control for these factors statistically, if needed.

D.6. Statistical methods

D.6.1. Statistical power: The power analysis for this study was completed with primary focus on the three hypotheses that comprise Specific Aim 1. We assumed the following race by SES interaction effect sizes for clinical pain severity (Cohen’s $f = .24$), perceived disability (Cohen’s $f = .19$), and functional performance difficulty (Cohen’s $f = .21$) derived from our pilot data. Effect size conventions are .10 (small), .25 (medium), and .40 (large). Probability value was set at .05 and the desired power was set at .85. According to these parameters and effect sizes, a total sample size of 240 participants is required to detect all of the race by SES interaction effects hypothesized for Specific Aim 1 (**Table 5**). These 240 participants will be allocated to four groups, such that there will be 60 low SES Blacks, 60 high SES Blacks, 60 low SES Whites, and 60 high SES Whites. Group sizes of 60 will provide greater than 95% power for detecting pair-wise differences while probing interaction effects based upon alpha level set as two-tailed $.05/6$ contrasts = .008 and Cohen’s d ranging from 0.83 to 1.90 (see C.2.1. above). We plan to over-enroll by 10% to accommodate for participant attrition. Therefore, 268 participants will be recruited with the expectation that at least 240 will complete.

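### Heat-test site order is randomised but is not a named term in the Aim 2 and Aim 3 models; adding it would be a small, cheap gain in precision

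*Combined protocol and SAP*

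**What the plan says.** Section D.2.4 (Heat Testing Procedures) sets the order of the two heat-test sites at random: "Thermal stimuli will be delivered to the lumber region (i.e., most affected pain site) and to the non-dominant forearm, in randomized order". It does not say how the order is generated, or whether it is kept in the data set.

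Section D.6.2 puts endogenous pain modulation under Specific Aim 2: "These hypotheses will be tested using 2x2 ANCOVAs in the same manner indicated in Specific Aim 1". That means race, SES, their interaction and covariates. The candidate covariates begin with medication for pain, sex and age, and the list ends as follows: "engagement in treatments during the 4 week follow up period, and others as appropriate and will be considered as statistical controls". Site order is not named, though the open-ended last item would allow it.

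Under Specific Aim 3, temporal summation is given as an example of a predictor, in regressions fitted separately for Black and White participants with SES as moderator. Order is not mentioned there either.

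Section D.6.1 bases the sample size on Aim 1 only and gives no effect size for any heat measure.

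**The concern.** For either site, about half the participants are tested on fresh skin and half after a painful series at the other site. If people habituate or sensitise between the two series, site-specific heat temporal summation carries a first-versus-second component unrelated to race or SES. A model that leaves out order counts that component as unexplained variation, although the study itself generated it and could identify it exactly.

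In Aim 2 the stake is precision. In Aim 3 there is a second, small effect: temporal summation is on the predictor side, so order variance acts like measurement error and weakens the estimated association with the outcome. The heat measures have no sample-size margin of their own to absorb such losses.

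**Working it through.** **Inputs from the plan (D.6.1).** 240 completers, 60 in each of four cells. "Probability value was set at .05 and the desired power was set at .85". The smallest Aim 1 interaction effect is f = .19. It is borrowed here because none is given for heat testing.

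**Assumed input.** Order effect d, in units of the order-free residual SD, of 0.3, 0.5 or 0.7. The documents give no value, and zero is possible.

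**The plan's own figure.** D.6.1 says "a total sample size of 240 participants is required to detect all of the race by SES interaction effects hypothesized for Specific Aim 1". The check uses the noncentral F for a 2x2 interaction, with 1 and N − 4 df and noncentrality N × f². At N = 240 and f = .19 the noncentrality is 240 × .0361 = 8.664 and power is .834. Reaching .85 at exactly f = .19 takes N = 251. At f = .1942, which rounds to .19, N = 240 gives .85, so rounding can explain the gap. That is a separate matter. The reference power here is .834.

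**Aim 2: loss from omitting order.** A 50:50 factor of size d has variance d²/4, so residual variance is multiplied by k = 1 + d²/4 and the noncentrality becomes 8.664/k.

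| d | k | Noncentrality | Power | Loss (points) | 240 × d²/4 |
|---|---|---|---|---|---|
| 0 | 1 | 8.664 | .834 | 0 | 0 |
| 0.3 | 1.0225 | 8.473 | .826 | 0.8 | 5 |
| 0.5 | 1.0625 | 8.154 | .812 | 2.3 | 15 |
| 0.7 | 1.1225 | 7.718 | .790 | 4.4 | 29 |

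The last column is the number of extra participants that would offset the added variance. The 1 df spent on an order term leaves power at .834 to three decimals.

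**Is there bias?** Randomised order is independent of race and SES. In 20,000 simulated trials per setting, with order assigned by simple randomisation and left out of the model, the type I error of the interaction test was .049, .050 and .048 at d = 0.2, 0.5 and 0.8. With an order term it was .050 each time.

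**Is chance imbalance between cells a further harm?** No. Take d = 0.5. Without order variance, the interaction contrast has SE √(4/60) = 0.258. Under simple randomisation, imbalance shifts it by a random amount with SD 0.5 × 2 × √(.25/60) = 0.065. Then √(0.258² + 0.065²) = 0.266, which equals √(1.0625 × 4/60), the SE the unadjusted model already reports. Imbalance and residual noise are one quantity.

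**Aim 3: attenuation.** Take order as the only added noise in the predictor, and ignore that predictor's correlation with other terms. The slope is then multiplied by 1/k, that is .978, .941 or .891 at d = 0.3, 0.5 or 0.7. The shrinkage is about 2%, 6% or 11%, in models of about 120 participants each.

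**The case against.** The strongest reply is that randomising site order is itself the control for order effects. It protects the race by SES comparison, and an order term is an optional refinement whose value rests wholly on an assumed effect. The covariate list is open, so the analyst could add order anyway. If temporal summation were averaged over the two sites, everyone would contribute one first and one second series, and an order effect equal at both sites would cancel.

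Much of this stands. There is no threat to validity in Aim 2, and the gain may be nil. But permission to add a covariate is not a commitment, and adding it after seeing the data is weaker than naming it beforehand. The plan does not say that the sites will be averaged.

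Three stronger readings are tempting, and the documents do not support them:

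- *The order is unbalanced across the race by SES cells.* D.2.4 is silent on whether the list is simple, blocked or stratified. Even simple randomisation would add no harm beyond the variance already counted.
- *Order should be blocked within recruitment strata.* D.1.2 defines those strata by the poverty line, while D.6.2 forms the analysis cells by a Hollingshead split. Such blocking would not guarantee balance where it is wanted.
- *The same fault affects conditioned pain modulation, because* "immediately afterwards PPTs will again be assessed at the testing sites". The order of the pressure sites is not stated. If it is the same for everyone, it adds no variance between participants, and nothing in the documents lets its effect be sized.

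**Conclusion.** The point holds as a minor matter of precision. The plan randomises heat-site order but names it in neither the Aim 2 ANCOVAs nor the Aim 3 regressions, so any order effect remains as noise. For an assumed effect of 0.3 to 0.7 SD, the Aim 2 cost is 2% to 12% more residual variance and about 1 to 4 power points. The Aim 3 cost is slope attenuation of about 2% to 11%. These figures rest on the assumed effect, on a 50:50 split of orders, on f = .19 carried over from Aim 1, and on analysing each site separately. The Aim 1 outcomes on which the study was sized are not affected. It would be wrong to conclude that the Aim 2 group comparisons are biased or that their error rate is inflated.

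**What to change.** Record the randomised site order for each participant. In D.6.2, pre-specify it as a two-level factor (site tested first or second) in every site-specific heat temporal summation model in Aims 2 and 3. State in D.2.4 how the order is generated. If testing is already complete, the term can still be used wherever order was recorded.

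The cost is one recorded field and 1 df per model, with no added burden on participants. In an Aim 3 model with a temporal summation by SES product, an optional order by SES term, at one further df, would also clear the product of order noise.

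### Mechanical temporal summation is scored as percent change from one rating of a fixed filament; the score is undefined at a first rating of 0 and unstable near 0, and no companion analysis is planned.

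*Combined protocol and SAP*

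**What the plan says.** D.2.4 (Punctate Mechanical Pain) applies the same 300 g filament to every participant, at the lumbar region and the back of the non-dominant hand. At each site there is one rating after a single contact and one after 10 contacts. The score is then defined: "The percent change (increase) between pain ratings for the single versus multiple contacts reflects temporal summation of mechanical pain". No repeat ratings are described, and no step ensures that the single contact is painful for the individual. The cold stimulus in the same section is treated differently. It is "tailored for each participant to achieve a stimulus that produces moderate pain (i.e. a rating of 40-60 on the 0-100 scale".

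In D.6.2, endogenous pain modulation is an Aim 2 outcome: "These hypotheses will be tested using 2x2 ANCOVAs in the same manner indicated in Specific Aim 1". Under Aim 3 the plan gives as an example a model of "whether endogenous pain modulatory processes (e.g., CPM and TS) predict functional performance (e.g., SPPB and TUG", and "Within each model the SES variables will be added to examine interaction effects (i.e., moderation".

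Two general provisions come near the issue. One is descriptive: "Data analysis will begin with calculating and comparing measures of central tendency (sample mean, sample median) and dispersion (sample variance, interquartile range". The other concerns covariates: "Confounding variables may include age, sex, pain medication use, engagement in treatments during the 4 week follow up period, and others as appropriate". Neither D.2.4 nor D.6.2 says how a first rating of 0, or close to 0, is scored.

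**The concern.** The denominator is a single self-reported rating that can be zero or very small. A participant who rates the first contact 0 cannot be scored by the stated rule, so dropping, offsetting or re-scoring that person is left to be decided once the data are visible.

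Among the rest, a few very low first ratings produce enormous scores. Both planned uses are least-squares models, so those few people can dominate an Aim 2 cell mean or an Aim 3 slope, and a real difference can be missed.

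The score also depends on the first rating itself. If racial groups differ in how painful one contact feels, percent change can show a difference in summation where there is none. In a study of disparities that would be a wrong statement about mechanism.

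**Working it through.** **Inputs from the documents.** Percent change, one first rating per site, fixed filament (D.2.4). Cell sizes: "there will be 60 low SES Blacks, 60 high SES Blacks, 60 low SES Whites, and 60 high SES Whites" (D.6.1), so 240 in all. Least-squares models (D.6.2). The plan states no effect size, SD or power for temporal summation, so there is no figure of its own to reproduce.

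**Inputs assumed.** A 0-100 scale: it is named for the cold stimulus (D.2.4) and for pain during functional tasks (D.4.2), but not in the filament text. All rating distributions are assumed.

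**1. The score.** Score = 100 × (rating after 10 contacts − first rating) / first rating. For a 20-point rise:
- from 1: 100 × 20/1 = 2000%
- from 10: 100 × 20/10 = 200%
- from 40: 100 × 20/40 = 50%
- from 0: division by zero, no score

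**2. How many zeros.** If first ratings are normal, rounded and cut at 0, the share of zeros is Φ((0.5 − mean)/SD).

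| Assumed mean (SD) | Share of zeros | Of 240 |
|---|---|---|
| 10 (12) | Φ(−0.79) = 21% | 51 |
| 20 (15) | Φ(−1.30) = 10% | 23 |
| 30 (15) | Φ(−1.97) = 2.5% | 6 |
| 40 (15) | Φ(−2.63) = 0.4% | 1 |
| 50 (15) | Φ(−3.30) = 0.05% | 0 |

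**3. Simulation set-up.** 60 per cell; two-sided .05; ratings rounded and clipped to 0-100; first-rating SD 15, of which 0, 10, 20 or 30% of the variance is noise. Additive summation: increment normal, mean 15, SD 15. Proportional summation: rating × (1 + 0.6 × lognormal, log SD 0.6). Percent change drops zeros. The comparator for Aim 2 is the 10-contact rating with the single-contact rating as covariate.

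**4. Aim 2 power, equal first ratings (means 20-40).** True effects: race +6 points or a 1.4-fold increment; interaction, one cell +12 points or 1.8-fold.

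| Summation | Percent change | Adjusted |
|---|---|---|
| Additive | 15-45% | 79-88% |
| Proportional, 10-30% noise | 17-71% | 65-92% |
| Proportional, no noise | 90-97% | 90-96% |

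A separate simulation (additive change with mean 15, SD 12; interaction f = .19) gave .19-.41 for percent change and about .83 for the absolute change, with first-rating means from 10 to 40.

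**5. Aim 2 false positives, first ratings differing between cells, no true summation difference.**

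| Test | Summation | Percent change | Adjusted |
|---|---|---|---|
| Race main effect (gaps 5-15 points) | Additive | 11-76% | 5-47% |
| Race main effect (gaps 5-15 points) | Proportional | 4-12% | 5-89% |
| Race-by-SES interaction | Additive | 6-12% | 5-12% |
| Race-by-SES interaction | Proportional | 5-7% | 5-23% |

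For example, with race means of 20 and 30, percent change is falsely significant in 43% of runs and the adjusted analysis in 5% (additive, no noise). With proportional summation and 30% noise the figures are 5% and 63%. The adjusted analysis is at its worst at 30% noise, because a noisy covariate corrects only part of the first-rating gap.

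**6. Aim 3, SES moderation within one race (60 low, 60 high SES; true correlation .5 against 0).** The comparator is the difference score with the single-contact rating in the model, each with its SES interaction. Power for percent change against adjusted: 21-53% and 71-81% (additive); 12-43% and 28-59% (proportional with noise); 68-72% and 61-68% (proportional, no noise). With equal true correlations of .3 and equal first ratings, false moderation is 5-13% for percent change and 4-6% adjusted. Under additive summation, the three most extreme percent-change scores carry 45-74% of the predictor's sum of squares, against 15-27% for the difference score.

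**7. Requiring both analyses to be significant in the same direction.** This cuts false positives to 0-3.5%, but blocks true findings. With first ratings of 20 and 30, additive summation and truly greater summation in the higher-rating group, power under that rule is about 0.5%, against 87-98% for the adjusted analysis. In the reverse direction it loses 13-49 points against percent change.

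**The case against.** Percent change is a legitimate score. Where summation is proportional and the first rating is not noisy, it matches the adjusted analysis in Aim 2 and slightly exceeds it in Aim 3. The adjusted analysis can mislead more, reaching 89% false positives for race in the worst case against 76%. This stands, and it is why percent change should be kept. A reader might infer that it is simply the wrong score and should be replaced; neither the documents nor the figures support that.

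A reader might also infer that the planned interaction tests are badly inflated. They are not: percent change gives 5-12% there, and the high rates belong to the race main effect under assumed gaps. The main effect still matters, because Aim 2 hypothesises racial and SES differences.

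Every distribution is assumed. D.2.4 describes its stimuli as painful, and one site is the affected region, which makes very low first ratings less likely. At first-rating means of 40-50, only 0 or 1 of 240 would be zero. So the documents do not support saying that many participants will be unscorable. They do not rule out zeros either, and at a mean of 40 with additive summation the power loss remains.

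The procedure cites the team's earlier studies, which may contain a scoring convention. That cannot be checked here, and the plan states none. The descriptive step could reveal skew, and the open covariate list could admit the single-contact rating, but neither scores a zero.

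Finally, Aim 3 names temporal summation only as an example and does not say whether heat or mechanical. The Aim 3 part therefore applies only where the mechanical score is used.

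**Conclusion.** The point holds as a defect in a stated scoring rule for a secondary measure. That a first rating of 0 has no score, and that scores explode near 0, needs only that such ratings are allowed. The consequences for power and false positives are conditional on assumed ratings: large if summation is additive, substantial if the first rating is noisy, and absent if summation is proportional and the first rating is noise-free. A first-rating gap between races can be mistaken for a summation difference, mainly in the race main effect.

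It would go too far to read this as weakening the trial's main results. Aim 1 does not use the score, and the sample size in D.6.1 was set on Aim 1. CPM is also a percent change, but its denominator is a pressure threshold rather than a pain rating. D.2.4 states no scoring formula for heat summation, so nothing is concluded about it. The change is worth making because both ratings are already collected.

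**What to change.** In D.2.4 and D.6.2, for mechanical summation at each test site:

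1. Keep percent change for participants with a non-zero first rating. State that a first rating of 0 has no percent-change score. Report the number of zeros and the first-rating distribution by race-by-SES cell.
2. Beside it, pre-specify an analysis of all participants. In Aim 2, use the 10-contact rating in the planned 2x2 ANCOVA with the single-contact rating as covariate. In Aim 3, where mechanical summation is the predictor, use the difference score with the single-contact rating also in the model, each with its SES interaction.
3. Report both estimates with intervals. Where they disagree and first ratings differ between cells, state that a summation difference cannot be separated from a first-rating difference.
4. Do not require both analyses to be significant before a difference may be claimed. That nearly removes power when the group with higher first ratings also summates more.

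Cost: a few sentences, one extra analysis per test site and a more cautious conclusion when the two disagree. No new data are needed. The adjusted analysis is itself biased when first ratings differ and are noisy, so it stands beside percent change and does not replace it.
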